#### 16.2.1.2. Immune Response, Serogroup B Indicator Strains (measured by hSBA)

The immune response to the MenABCWY vaccine (0,6-month schedule) against *N. meningitidis* serogroup B indicator strains:

- **M14459** for factor H binding protein [fHbp] antigen
- **M13520** for NHBA antigen
- **96217** for Nad A antigen; and
- **NZ98/254** for PorA P1.4 antigen

will be demonstrated using:

- Logarithmically transformed (base 10) hSBA titers
- The percentages of participants with hSBA titers  $\geq$ LLOQ for each and all serogroup B indicator strains at baseline (Day 1, Month 0) and at 1 month after the last vaccination (Day 211, Month 7) for the ABCWY group. For the ‘all’ serogroup B indicator strains to be considered as satisfying the ‘ $\geq$ LLOQ’ criteria, all 4 of the serogroup indicator strains hSBA titers must be  $\geq$ LLOQ.
- The percentages of participants with 4-fold rise (refer to Section 6.6) in hSBA titers against each *N. meningitidis* serogroup B indicator strains at 1 month after the last vaccination (Day 211, Month 7) relative to baseline (Day 1, Month 0) for the ABCWY group.

---

Document: C:\ProgramData\activePDF\Temp\DocConverter\API\input\99638a57dafd\$76D9DDEF7D8D4E7C  
B4DEE6C228977964.docx

Author: PPD

Version Number:

Final 5.0

**CONFIDENTIAL** Version Date:

05SEP2022

## 16.2.2. MISSING DATA METHODS FOR SECONDARY IMMUNOGENICITY VARIABLES

Refer to Section [7.3](#)

## 16.2.3. ANALYSIS OF SECONDARY IMMUNOGENICITY VARIABLES

### 16.2.3.1. Immune Response Analysis, Serogroups A, C, W and Y (measured by hSBA)

For each of the 4 *N. meningitidis* serogroups A, C, W, and Y the percentages of participants with hSBA titers  $\geq$ LLOQ and the corresponding exact 2-sided 95% CIs based on Clopper-Pearson method ([Clopper](#)) will be calculated at baseline (Day 1, Month 0), and at 1 month after the **first** (Day 31, Month 1) and the **last** vaccination (Day 211, Month 7) for the ABCWY group, and at baseline (Day 1, Month 0) and 1 month after the single MenACWY vaccination for the ACWY group (Day 31, Month 1).

The titers at baseline (Day 1, Month 0), at 1 month after the **first** (Day 31, Month 1) and the **last** vaccination (Day 211, Month 7) for the ABCWY group, and at 1 month after the single MenACWY vaccination (Day 31, Month 1) in the ACWY group, will be logarithmically transformed (base 10) to fulfill the normal distribution assumption.

GMTs and 95% CIs will be calculated by exponentiating (base 10) the least squares means and the lower and upper limits of the 95% CIs of the log-transformed titers (base 10) obtained from:

- an ANOVA with factors for vaccine group and country.
- an ANCOVA with baseline titers as a covariate, and factors for vaccine group and country.

GMRs (post vaccination/baseline titer) and associated 2-sided 95% CIs will be computed for each group and for each serogroup at each visit. GMRs will be calculated by exponentiating (base 10) the least squares means and the lower and upper limits of the 95% CIs of the log-transformed titers (base 10) obtained from an ANOVA with factors for vaccine group and country.

Additionally, GMTs and GMRs group ratios between the 2 vaccine groups and their respective 95% CIs will be computed by exponentiating the difference of the least square means of the log-transformed titers and the lower and upper limits of the 95% CIs on the difference obtained from the ANOVA model above.

---

Document: C:\ProgramData\activePDF\Temp\DocConverter\API\input\99638a57dafd\$76D9DDEF7D8D4E7C  
B4DEE6C228977964.docx

Author: PPD

Version Number:

Final 5.0

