- ⁴ For the N Men B test strains: samples from 189 participants in the ABCWY group and 20 participants in the control group to maintain the study blinding at all time points (Day 1, Day 31, and Day 211). For the N Men A, C, W, Y serogroups: samples from all study participants will be tested at Day 1 and Day 31, and samples from 250 participants in the ABCWY group and 20 participants in the control group to maintain the study blinding will be tested at Day 211. Evaluation of the tertiary objective is participant to the availability of samples and may or not be performed.

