9.4.4 Secondary Endpoints

9.4.4.1 Immune Response N. Meningitidis Serogroups A, C, W, and Y (Measured by hSBA)

Analysis set: The analysis will be based on the FAS.

Statistical method: For each of the 4 *N. meningitidis* serogroups A, C, W, and Y the percentages of participants with hSBA titers \geq LLOQ and the corresponding exact 2-sided 95% CIs based on Clopper-Pearson method ([Clopper and Pearson, 1934](#)) will be calculated for ABCWY and ACWY study groups. Refer to [Section 9.4.3.1](#) for the definition of 4-fold rise for the Men A, C, W, and Y evaluation.

Geometric mean titers and associated 2-sided 95% CIs will be computed for each group and for each strain at each visit. The titers at baseline (Day 1, Month 0), at 1 month after the first (Day 31, Month 1) and the last vaccination (Day 211, Month 7) for the ABCWY group, and at 1 month after the single MenACWY vaccination (Day 31, Month 1) in the ACWY group, will be logarithmically transformed (base10) to fulfill the normal distribution assumption.

Geometric mean titers and 95% CIs will be calculated by exponentiating (base 10) the least squares means and the lower and upper limits of the 95% CIs of the log-transformed titers (base10) obtained from a 2-way Analysis of covariance (ANCOVA) with factors for vaccine group and country. The ANCOVA will include baseline titers as covariate, and it will be performed to take into consideration the possible effect of these on the post-vaccination titers.

Geometric mean ratios (GMRs) (post-vaccination/baseline titer) and associated 2-sided 95% CIs will be computed for each group and for each strain at each visit. Geometric mean ratios will be calculated by exponentiating (base10) the least squares means and the lower and upper limits of the 95% CIs of the log-transformed titers (base10) obtained from a 2-way ANOVA with factors for vaccine group and country.

Additionally, GMTs and GMRs group ratios between the 2 intervention groups and their respective 95% CIs will be computed by exponentiating the difference of the least square means of the log-transformed titers and the lower and upper limits of the 95% CIs on the difference obtained from the ANCOVA/ANOVA model above.

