### 2.5.2. SECONDARY IMMUNOGENICITY ENDPOINTS

The immune response to MenABCWY (0,6-month schedule) and MenACWY (single dose) vaccines against *N. meningitidis* serogroups A, C, W, and Y, at pre-vaccination (Day 1, Month 0) and 1 month after the **first and last** MenABCWY vaccinations and 1 month after the single MenACWY vaccination will be demonstrated for participants in the Full Analysis Set (FAS, as defined in Section 5.4) by:

- The percentages of participants with hSBA titers  $\geq$  Lower Limit of Quantitation (LLOQ) against serogroups A, C, W, and Y:
  - at baseline (Day 1, Month 0) and at 1 month after the first (Day 31, Month 1) and the last vaccination (Day 211, Month 7) for the ABCWY group, and
  - at baseline (Day 1, Month 0) and 1 month after the single MenACWY vaccination for the ACWY group (Day 31, Month 1).
- The geometric mean titers (GMTs) against serogroups A, C, W, and Y:
  - at baseline (Day 1, Month 0) and at 1 month after the first (Day 31, Month 1) and the last (Day 211, Month 7) vaccinations for the ABCWY group, and
  - at baseline (Day 1, Month 0) and 1 month after the single MenACWY vaccination for the ACWY group (Day 31, Month 1).
- The geometric mean ratios (GMRs) against serogroups A, C, W, and Y:
  - at 1 month after the first (Day 31, Month 1) and the last vaccination (Day 211, Month 7) for the ABCWY group as compared to baseline (Day 1, Month 0) and
  - at 1 month after the MenACWY vaccination (Day 31, Month 1) for the ACWY group as compared to baseline (Day 1, Month 0).

The immune response to the MenABCWY vaccine (0,6-month schedule) against *N. meningitidis* serogroup B indicator strains, at pre-vaccination (Day 1, Month 0) and at 1 month after the **last** MenABCWY vaccination will be demonstrated for participants in the FAS (as defined in Section 5.4) from:

- The percentages of participants with hSBA titers  $\geq$  LLOQ for each and all serogroup B indicator strains at baseline (Day 1, Month 0) and at 1 month after the last vaccination (Day 211, Month 7) for the ABCWY group.

Document: C:\ProgramData\activePDF\Temp\DocConverter\API\input\99638a57dafd\$76D9DDEF7D8D4E7C B4DEE6C228977964.docx

Author: PPD

Version Number: Final 5.0

**CONFIDENTIAL** Version Date: 05SEP2022

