### 3.3. CHANGES TO ANALYSIS FROM PROTOCOL

The visit window in the protocol is -5/+14 days for visits 2, 3 and 4. For the statistical analysis this window will be -7/+28 days for each visit.

There are no other changes to planned analyses in the protocol. However, during special circumstances such as the COVID-19 pandemic, the specific guidance from local public health and other competent authorities regarding the protection of individuals' welfare will be applied. For the duration of such special circumstances, some measures may impact the data and analysis:

- Delayed FPI
- Protocol deviations due to COVID-19
- Missed visits due to COVID-19
- Missed or modified assessments
- Treatment interruptions or delays
- Early study discontinuation or withdrawals due to having COVID-19 or COVID-19 related issues
- Adverse events or SAEs due to COVID-19

The number and percentage of participants experiencing any of the COVID related consequences listed above will be presented.

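### The SAP takes the post-vaccination A, C, W and Y GMT group ratios from the unadjusted ANOVA, whereas the protocol's only GMT model is the baseline-adjusted ANCOVA, and the change is not declared

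*SAP*

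**What the plan says.** **Protocol 9.4.4.1.** GMTs for serogroups A, C, W and Y, with their 95% CIs, are back-transformed least-squares means "obtained from a 2-way Analysis of covariance (ANCOVA) with factors for vaccine group and country". Baseline titre is the covariate, included because it may affect the post-vaccination titre. GMRs (post-vaccination over baseline) come from a two-way ANOVA on vaccine group and country. The ratios between groups, for GMTs and GMRs alike, rest on the difference in least-squares means and the limits "on the difference obtained from the ANCOVA/ANOVA model above".

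**SAP 16.2.3.1.** GMTs are obtained from two separately listed models: an ANOVA on vaccine group and country, and "an ANCOVA with baseline titers as a covariate, and factors for vaccine group and country". GMRs come from the ANOVA. Both kinds of group ratio then use the least-squares mean difference and "the lower and upper limits of the 95% CIs on the difference obtained from the ANOVA model above".

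**SAP 3.3.** After the widened visit windows, the section states: "There are no other changes to planned analyses in the protocol". The SAP modification history does not list a change of model either.

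**Data available.** Under Protocol Table 11, footnote 4, for A, C, W and Y "samples from all study participants will be tested at Day 1 and Day 31". At Day 211 the plan is to test "samples from 250 participants in the ABCWY group and 20 participants in the control group to maintain the study blinding".

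**The concern.** The protocol has no ANOVA for GMTs. The natural reading of its combined ANCOVA/ANOVA phrase is therefore ANCOVA for the GMT ratio and ANOVA for the GMR ratio. The SAP uses the two model names for two different analyses and then names only the ANOVA as the source of both ratios. A programmer following the text would produce an unadjusted GMT ratio with its CI and would not produce the adjusted CI that the protocol implies.

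Three things are at stake:

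- **Fidelity.** The headline between-group GMT comparison would come from a different model than the protocol's, with no declaration.
- **Precision.** The unadjusted CI is wider to the extent that baseline predicts response.
- **Chance imbalance.** Minimisation accounts for country only, so baseline titre is balanced only by chance. The unadjusted ratio keeps a share of any imbalance.

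The SAP's other outputs do not clearly fill the gap. The per-group ANCOVA GMTs yield the adjusted point estimate, but not in general its CI. The GMR ratio is a change-score contrast with a different CI.

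**Working it through.** The documents give no precision or power figure for these ratios, so there is nothing of the plan's to reproduce. The check is a comparison of texts, followed by the size of the consequence.

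**1. Models side by side**

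| Quantity | Protocol 9.4.4.1 | SAP 16.2.3.1 |
|---|---|---|
| GMT per group | ANCOVA | ANOVA and ANCOVA |
| GMR per group | ANOVA | ANOVA |
| GMT group ratio | ANCOVA/ANOVA phrase; only the ANCOVA is defined for GMTs | ANOVA |
| GMR group ratio | ANCOVA/ANOVA phrase; only the ANOVA is defined for GMRs | ANOVA |

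Only the GMT group ratio differs. At baseline an ANOVA is the sensible choice, because baseline titre cannot be its own covariate. The point is therefore confined to post-vaccination ratios.

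**2. CI width.** Let r be the within-group correlation of baseline and post-vaccination log titres (not in the documents, so shown as a range). ANOVA width divided by ANCOVA width is 1/√(1 − r²):

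| r | 0 | 0.2 | 0.3 | 0.5 | 0.6 |
|---|---|---|---|---|---|
| ratio | 1.00 | 1.02 | 1.05 | 1.15 | 1.25 |

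A simulation with four countries, normal log titres and equal SDs gave the same values at r = 0, 0.3, 0.5 and 0.6, both for 542 vs 542 and for 225 vs 542. On the ratio scale, with 542 per group and an assumed log10 SD of 0.6, the ANOVA CI is the estimate times or divided by 10^(1.96 × 0.6 × √(2/542)) = 1.18. The ANCOVA factor is 1.17 at r = 0.3 and 1.15 at r = 0.5.

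**3. Chance baseline imbalance.** A 1.96-SE imbalance, in baseline SD units, is 1.96 × √(1/a + 1/b):

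- Day 31 contrast: 603 vs 603 gives 0.113; 542 vs 542 gives 0.119.
- ABCWY Day 211 against ACWY Day 31: 250 vs 603 gives 0.147; 225 vs 542 gives 0.155.

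Such an imbalance moves the ANOVA log ratio by r times its own CI half-width and the ANCOVA log ratio by about 0. With SD 0.6 and 542 per group, the shift factor is 10^(r × 0.6 × 0.119): 1.05 at r = 0.3 and 1.09 at r = 0.5.

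**4. Can the adjusted CI be recovered from other outputs?**

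- *From the per-group ANCOVA CIs.* The least-squares means share the country error if countries are weighted equally. For 542 vs 542, treating the two CIs as independent gives 1.00 times the correct width with four equal countries, about 1.07 with shares of 40/30/20/10%, and about 1.24 with 60/20/15/5% (assumed shares). With observed-margin weights the factor is 1.00. The SAP does not state the weighting.
- *From the GMR ratio.* With equal SDs its CI is √(2/(1 + r)) times the ANCOVA CI: 1.41 at r = 0, 1.24 at 0.3 and 1.15 at 0.5. Its sensitivity to imbalance has slope r − 1, against 0 for the ANCOVA.

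**5. Which visits are contrasted.** Neither document's ratio sentence names them. If Day 211 were contrasted by visit, the comparator would be about 20 controls. The unadjusted half-width would be 1.96 × √(1/250 + 1/20) = 0.455 SD, against 0.147 SD for 250 vs 603, or 3.1 times wider. The secondary endpoints (SAP 2.5.2) use ACWY at Day 31.

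**The case against.** The strongest case is that this is a small consistency edit:

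- The group ratio is not in the endpoint lists. It appears only as an additional computation, with no margin, alpha or decision attached, and both estimators are unbiased under randomisation. All of this stands and limits the weight of the point.
- The protocol's phrase has no 'respectively', and its GMT model cannot serve for baseline GMTs, so the SAP's added ANOVA fills a real gap. This is true, but it justifies an ANOVA at baseline only. For post-vaccination GMTs the protocol offers nothing but the ANCOVA.
- SAP 7.2 describes the GMT/GMR vaccine-effect model as containing country and vaccine only, so the ANOVA may be deliberate. If so, the defect is the missing declaration in SAP 3.3, and declaring it would be a sufficient remedy. The wording confirms the literal ANOVA reading; it does not remove the conflict with the protocol.
- The table shells mentioned in SAP Section 8 might show the ANCOVA ratio. They are not in the text available, so one can say only that the SAP text does not specify it. If they do show it, the text should match.
- The gain may be small. r is unknown, and imputing values below LLOQ weakens it: with half of baselines below LLOQ (assumed), r = 0.5 becomes 0.45 and the width ratio falls from 1.15 to 1.12. Also, the CI-rebuild penalty disappears under observed-margin weights. Both stand. They reduce the size but do not make the two documents agree.
- Naming visit contrasts goes beyond the defect. It does, and it is a separate clarification, included because the same sentence leaves the comparator open.

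**Conclusion.** The concern holds. For post-vaccination A, C, W and Y GMT group ratios, the SAP names a different model from the only one the protocol defines for GMTs, and SAP 3.3 states that nothing but the visit windows has changed. GMR ratios agree between the documents.

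The consequence is modest: no loss of precision at r = 0, and a CI about 5% wider at r = 0.3 and 15% wider at r = 0.5, together with retention of a share r of any chance baseline imbalance. These figures assume equal SDs and roughly normal log titres, and they shrink with heavy censoring at the LLOQ. The results concerned are descriptive, secondary and on the FAS; the co-primary non-inferiority conclusions do not depend on them. It should be corrected because the discrepancy is plain in the text and cheap to remove.

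**What to change.** In the last paragraph of SAP 16.2.3.1, keep the exponentiated least-squares mean differences but state that:

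- post-vaccination GMT ratios and their CIs come from the ANCOVA;
- GMR ratios, and GMT ratios at baseline, come from the ANOVA;
- the post-vaccination contrasts are ABCWY Day 31 and ABCWY Day 211, each against ACWY Day 31.

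The ANOVA GMT ratio may be shown alongside, so that participants without a baseline titre are included. If the ANOVA is intended as the source of the GMT ratio, declare and justify that in SAP 3.3 instead. Optionally, clarify SAP 7.2 so that it does not appear to exclude the baseline covariate.

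**Cost.** One sentence is changed and one added. The ANCOVA is already planned and Day 1 titres are planned for everyone, so only the CI of its group difference is added to the output. The downside is that participants lacking a baseline titre for a serogroup drop out of the adjusted contrast. If they are missing at random with share m, the ANCOVA variance relative to the ANOVA is (1 − r²)/(1 − m), so the ANCOVA remains more precise while m is below r²: 4% at r = 0.2, 9% at 0.3 and 25% at 0.5. At r = 0 it gains nothing.

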**CONFIDENTIAL**

Version Date:

05SEP2022

[figure not shown]
16.2.3.2. Immune Response Analysis, Serogroup B Indicator Strains (measured by hSBA)

For *N. meningitidis* B indicator strains (M14459 for factor H binding protein [fHbp] antigen, M13520 for NHBA antigen, 96217 for NadA antigen and NZ98/254 for PorA P1.4 antigen):

- the percentages of participants with hSBA titers  $\geq$ LLOQ for each and all serogroup B indicator strains, and the corresponding exact 2-sided 95% CIs based on Clopper-Pearson method (Clopper) will be calculated for the MenABCWY vaccine group at at baseline (Day 1, Month 0), and at 1 month after the **last** vaccination (Day 211, Month 7); and
- the percentage of participants with 4-fold rise (refer to Section 6.6) relative to baseline for each serogroup B indicator strains, and the corresponding exact 2-sided 95% CIs based on Clopper-Pearson method (Clopper) will be calculated for the MenABCWY vaccine group at at 1 month after the **last** vaccination (Day 211, Month 7).

[figure not shown]
GMTs and associated 2-sided 95% CIs will be computed for each serogroup B indicator strain at baseline (Day 1, Month 0), and at 1 month after the **last** vaccination (Day 211, Month 7) for the ABCWY vaccine group. The hSBA titers at baseline (Day 1, Month 0), and the hSBA titers at 1 month after the last vaccination (Day 211, Month 7) for the ABCWY group, will be logarithmically transformed (base 10) to fulfill the normal distribution assumption. For each *N. meningitidis* B test strain (M14459, M13520, 96217 and NZ98/254), the GMTs pre- and post-vaccination with their 95% CIs will be calculated by exponentiating (base 10) the means and the lower and upper limits of the 95% CIs of the log-transformed titers (base 10) values.

GMRs (post-vaccination/baseline titer) and associated 2-sided 95% CIs will be computed for each serogroup B indicator strain at 1 month after the **last** vaccination (Day 211, Month 7) for the ABCWY vaccine group, by exponentiating the corresponding log-transformed mean and 95% CI.

CCI

---

Document: C:\ProgramData\activePDF\Temp\DocConverter\API\Input\99638a57dafd\$76D9DDEF7D8D4E7C  
B4DEE6C228977964.docx

Author: PPD

Version Number: Final 5.0

**CONFIDENTIAL** Version Date: 05SEP2022

CCI

[figure not shown]
Document: C:\ProgramData\activePDF\Temp\DocConverter\API\Input\99638a57dafd\$76D9DDEF7D8D4E7C  
B4DEE6C228977964.docx

Author: PPD

Version Number: Final 5.0

**CONFIDENTIAL** Version Date: 05SEP2022

CCI

## 17. SAFETY OUTCOMES

The analysis of safety assessments in this study will include summaries of the following categories of safety data collected for each participant:

- Solicited administration site and systemic adverse events and indicators of solicited events.
- Unsolicited adverse events.

There will be no statistical comparisons between the vaccine groups for safety data, unless otherwise specified with the relevant section.

### 17.1. ADVERSE EVENTS

Adverse Events (AEs) will be coded using the current version of the MedDRA dictionary.

---

Document: C:\ProgramData\activePDF\Temp\DocConverter\API\Input\99638a57dafd\$76D9DDEF7D8D4E7C  
B4DEE6C228977964.docx

Author: PPD

Version Number: Final 5.0

**CONFIDENTIAL** Version Date: 05SEP2022

See APPENDIX 2 for handling of partial dates for AEs. In the case where it is not possible to determine if an AE started after the first vaccination or not, the AE will be considered to have started after the vaccination.

### 17.1.1. SAFETY COMPLETENESS ANALYSIS

#### Solicited events (solicited administration site events and solicited systemic events)

The safety completeness analysis on solicited events aims to identify participants who completed the eDiary, irrespective of severity. The analysis will show the number of participants with valid data by solicited event, for each vaccination.

Four summaries will be produced:

- The frequencies of participants who provide eDiary information by vaccine group.
- For each solicited event, the frequencies of participants with valid data will be presented by vaccine group and time point: Day 1, Days 2, 3, 4, 5, 6 and 7.
- For each type of solicited event (administration site, systemic), the frequencies of participants with valid data by vaccine group, aggregated over time points: Day 1 - Day 7.
- For each solicited event, the frequencies of participants with valid data by vaccine group, aggregated over time points: Day 1 - Day 7.

For the corresponding percentages, the denominator will be the respective numbers of exposed participants, i.e., participants who received a vaccination and were still in-study for that time point or time interval, irrespective of whether an eDiary was available or not. All analyses will be based on the ES.

### 17.1.2. SOLICITED EVENTS

For details please refer to Appendix 4 of the protocol. Solicited events will be summarized using the SSS.

Only solicited administration site (i.e., injection site pain, erythema, swelling, induration) and systemic (i.e., fever [temperature  $\geq 38.0^{\circ}\text{C}/100.4^{\circ}\text{F}$ ], nausea, fatigue, myalgia, arthralgia, headache) adverse events reported in the diary card will be analyzed.

---

Document: C:\ProgramData\activePDF\Temp\DocConverter\API\Input\99638a57dafd\$76D9DDEF7D8D4E7C  
B4DEE6C228977964.docx

Author: PPD

Version Number: Final 5.0

**CONFIDENTIAL** Version Date: 05SEP2022

Solicited events will be reported daily starting on Day 1 and until Day 7 after each vaccination a Day 1 and Day 181 using structured eDiaries, i.e. Day 1 to Day 7 and Day 181 to 187. The analyses of solicited events will be done based on three intervals after each vaccination: Day 1 - 3, Day 4 - 7 and Day 1 - Day 7. Solicited site administration or systemic adverse events extending beyond 7 days will be presented separately. In addition:

- A solicited administration site or systemic adverse event ongoing after 7 days following each vaccination; or
- A solicited administration site or systemic adverse event that leads to a visit to a healthcare provider (medically attended AE); or
- A solicited administration site or systemic adverse event leading to the participant withdrawing from the study or the participant being withdrawn from the study by the investigator (AE leading to withdrawal); or
- A solicited administration site or systemic adverse event that otherwise meets the definition of an SAE
- Will be recorded and presented as an unsolicited AE.

For erythema, swelling and induration, recorded originally as diameters (mm), the following categorization will be used to summarize the data:

- None (< 25 mm) vs. any ( $\geq$  25 mm)
- None (< 25 mm), Mild (25-50 mm), Moderate (51-100 mm) and Severe (>100 mm)

Body temperature will be broken down by route of measurement according to the recommendations of the Brighton collaboration ([www.brightoncollaboration.org](http://www.brightoncollaboration.org)) and will be summarized according to the 3 schemes described below:

- by 1.0 °C increments:
  - <36.0,
  - 36.0 - 36.9
  - 37.0 - 37.9

---

Document: C:\ProgramData\activePDF\Temp\DocConverter\API\input\99638a57dafd\$76D9DDEF7D8D4E7C  
B4DEE6C228977964.docx

Author: PPD

Version Number:

Final 5.0

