8.3.6 Adverse Events

8.3.6.1 Time Period and Frequency for Collecting AE and SAE Information

Solicited administration site and systemic events occurring during the 7 days (including the day of vaccination) following vaccination at Day 1 and Day 181, will be collected using a pre-defined participant eDiary (refer to the SoA [[Table 3](#)]). See [Appendix 1](#),

Glossary of Terms, for definitions of various types of AEs and to [Appendix 4](#) for further details on solicited AEs. Solicited administration site and systemic events that are ongoing after the 7-day reporting period will continue to be recorded in the eDiary until resolution or up to 30 days post-vaccination (i.e., recording period for unsolicited AEs) whichever occurs first and do not need to be entered as an AE in the AE eCRF or the participant's source document.

Any solicited AE that has not resolved within 30 days post-vaccination and is reported during clinic visits or safety follow-up calls will be entered into the subject's eCRF as an unsolicited AE. It will also be included in the subject's source documents at the site by the investigator/site staff as a verbally reported event. It will not be included in the Subject eDiary. These AEs will be analyzed as unsolicited AEs (i.e., in the Unsolicited Safety Set).

Unsolicited AEs are AEs that are not solicited using a participant eDiary occurring during the 30 days (including the day of vaccination) following vaccination at Day 1 and Day 181 (refer to the SoA [[Table 3](#)]), and must be recorded in the appropriate section of the eCRF, irrespective of intensity or whether or not they are considered vaccination-related.

The time period for collecting and recording AEs leading to vaccine/study withdrawal, medically attended AEs, SAEs, pregnancies, and AESIs will begin at Day 1 (i.e., the first receipt of study vaccines) and will end 6 months following administration of the last dose of investigational vaccine for each participant (i.e., study end). Refer to [Section 8.3.6.4](#) for instructions on reporting of SAEs, pregnancies, and AESIs.

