**CONFIDENTIAL**

Version Date:

05SEP2022

- 38.0 - 38.9
  - 39.0 - 39.9
  - $\geq 40.0^{\circ}$
- $<38.0, \geq 38.0^{\circ}\text{C}$  (i.e., 'no fever' versus 'fever')

Fever, defined as a body temperature of  $\geq 38^{\circ}\text{C}$  irrespective of route of measurement, will be integrated to the summaries as a systemic AE.

The analyses will encompass summaries of the data on five levels:

1. Daily reports of participants with solicited events.
2. Time of first onset of solicited events.
3. Solicited events, maximum event severity (i.e., severity grading scale as defined in Appendix 4 of the protocol) by event and interval Day 1 - 3, Day 4 - 7, and Day 1 - 7.
4. Duration of solicited events, excluding ongoing solicited events after Day 7.
5. Solicited events and indicators of solicited events, occurrence of at least one event by category (administration site, systemic) and interval Day 1 - 3, Day 4 - 7, Day 1 - 7 and extending beyond Day 7.

For studies using electronic diaries for the collection of solicited events, a solicited event will be considered present only when a daily recording of grade 1 or more is present. For each of the time points or time intervals presented in the summaries, only participants with at least one observation for the solicited events in the interval of interest will be considered.

The analysis of solicited events after first vaccination will be reported separately from the analyses of solicited events after second vaccination. When the occurrences of solicited events are summarized, each event recorded as having occurred during a specific period will be counted as only one occurrence regardless of the number of days on which it occurs

Level 1: Daily reports of solicited events

For each of the time points, only participants with at least one observation for the solicited events in the

---

Document: C:\ProgramData\activePDF\Temp\DocConverter\API\Input\99638a57dafd\$76D9DDEF7D8D4E7C  
B4DEE6C228977964.docx

Author: PPD

Version Number:

Final 5.0

**CONFIDENTIAL** Version Date:

05SEP2022

interval of interest will be considered. Data collected will be summarized (frequencies and percentages of participants) by vaccine group, solicited events, vaccination number and time point.

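### SAP 17.1.2 turns every solicited reaction lasting past 7 days into an unsolicited AE; on duration, the protocol does so only past 30 days and if reported, and SAP 3.3 does not declare the difference

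*SAP*

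**What the plan says.** **SAP 17.1.2 (Solicited Events)** gives four conditions joined by *or*. The first is "A solicited administration site or systemic adverse event ongoing after 7 days following each vaccination; or". The other three are that the reaction was medically attended, led to withdrawal, or met the SAE definition. The consequence, set as a final bullet, is "Will be recorded and presented as an unsolicited AE". The same section says that reactions "extending beyond 7 days will be presented separately", and its fifth summary level includes a category "Day 1 - 7 and extending beyond Day 7".

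**Protocol 8.3.6.1** treats reactions ongoing after the 7-day period differently. They "will continue to be recorded in the eDiary until resolution or up to 30 days post-vaccination", whichever comes first, and "do not need to be entered as an AE in the AE eCRF" or in the source document. The route to unsolicited status is narrower: "Any solicited AE that has not resolved within 30 days post-vaccination and is reported during clinic visits or safety follow-up calls" is entered in the eCRF as unsolicited and analysed in the Unsolicited Safety Set.

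**SAP 3.3** names the wider analysis visit window as the change from the protocol and says there are no others. **SAP 1** states that the SAP follows protocol amendment 3, whose text contains the 30-day rule.

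**The concern.** The two documents use different duration thresholds (7 days against 30), and the SAP drops the protocol's second condition, that the event be reported at a visit or call. The percentage of participants with any unsolicited AE in the 30 days after vaccination is a primary safety endpoint (SAP 2.5.4). If the SAP rule is followed, that percentage can include ordinary injection-site or systemic reactions that merely lasted longer than a week, which the protocol counts as solicited.

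There is also a data problem. SAP 17.1.3 takes the information for all unsolicited-AE summaries from the eCRF AE Form, but the protocol tells sites that these reactions need not be entered there. Whether a given reaction is counted may then depend on the habits of the site rather than on a definition.

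**Working it through.** No published figure has to be reproduced. The check compares the texts and then bounds the effect.

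**1. Side by side, by duration alone**

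| Solicited reaction with onset in the 7-day period | SAP 17.1.2 | Protocol 8.3.6.1 |
|---|---|---|
| Resolved by Day 7 | Solicited | Solicited |
| Ongoing after Day 7, resolved within 30 days | Unsolicited, and also in the separate solicited table | Solicited; eDiary only, no AE eCRF entry needed |
| Unresolved at 30 days, reported at a visit or call | Unsolicited | Unsolicited |
| Unresolved at 30 days, not reported | Unsolicited | Not made unsolicited |

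The documents disagree in the second and fourth rows.

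**2. Does other text reconcile them?**
- Protocol Appendix 4 requires eCRF entry of solicited events that are medically attended, lead to withdrawal or are SAEs. These match the SAP's other three conditions. The appendix has no 7-day criterion.
- The protocol glossary and the closing note of SAP 17.1.3 make solicited symptoms that *start* after the solicited period unsolicited. That concerns late onset, not persistence.

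**3. Does it reach the endpoint?** SAP 17.1.3 assigns unsolicited AEs to intervals by day of onset. Take a reaction that starts on Day 3 and ends on Day 12, with no medical visit, withdrawal or seriousness. Under the SAP, if it is in the eCRF, it falls in the Day 1 to 31 interval and the participant counts as having an unsolicited AE. Under the protocol the participant does not, unless another event qualifies.

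**4. Bounds.** The lower bound is 0, if no site enters such reactions. The upper bound is the share of participants who have a reaction ongoing after Day 7 that meets none of the other three conditions, is not both unresolved at 30 days and reported, and who have no other unsolicited AE in the interval. The documents give no rate for this. With *assumed* shares applied to the 603 planned per group:
- 1%: 603 × 0.01 = 6.03, so 0 to about 6 participants
- 5%: 603 × 0.05 = 30.15, so 0 to about 30
- 10%: 603 × 0.10 = 60.3, so 0 to about 60

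Each range runs from no site entry to full entry. These figures show scale only; they are not estimates, and the actual denominator is the Unsolicited Safety Set.

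**5. Interval length (minor).** SAP 17.1.3 uses Day 1 to Day 31 and Day 181 to Day 211. Inclusive lengths are 31 − 1 + 1 = 31 and 211 − 181 + 1 = 31 days, against an endpoint of 30 days including the day of vaccination. Only onsets on the 31st day are affected; after the second dose that is nominal Day 211, the day of the Visit 4 injection.

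**The case against.** The strongest case is that the harm may be nil. If sites enter only what the protocol requires, no 8-to-30-day reaction reaches the AE Form and the unsolicited tables do not change. Detailed eDiary instructions sit in a study reference manual that is not available here, and nothing in the documents shows that sites make optional entries. Safety is descriptive (SAP 17), and the longer reactions have their own table, so this could be read as one stale bullet.

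Much of that stands, and it limits the severity. It does not remove the contradiction. If nothing is entered, the SAP's rule cannot be carried out from the source it names; if some sites enter these reactions, the percentage departs from the protocol definition unevenly. Neither outcome is what the plan intends.

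The assumed rates are fairly criticised as uninformative about this trial, and they carry no weight in the conclusion. The document history is also only suggestive. Protocol Appendix 7 shows that Amendment 2 added the 30-day paragraph, and the SAP version made for that amendment lists only the co-primary promotion as a significant change. That is consistent with the paragraph not being carried over, but does not prove it.

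Two side issues are not pressed. The thirty-day footnote in protocol Table 12 sits on D31 and D211, but those are visit columns and the table's event rows are not legible in the available text. Events after the Visit 4 injection are largely covered by the relative-dose rule in SAP 17.1.3.

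**Conclusion.** The concern holds. On duration, the current SAP and the current protocol classify reactions persisting for 8 to 30 days differently, no other passage reconciles them, and SAP 3.3 states that there is no such change. The consequence is a primary safety percentage that may not follow the protocol definition and may vary with site practice. The increase lies between zero and an upper limit that the documents do not allow to be computed. A positive effect requires that some of these reactions are entered on the AE Form, or that programmers draw them from the eDiary. No hypothesis test or non-inferiority conclusion is affected and no reaction is hidden. It should be corrected before the safety tables are produced.

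**What to change.** In SAP 17.1.2, replace the 7-day bullet with the condition in protocol 8.3.6.1: still unresolved 30 days after vaccination and reported at a clinic visit or safety call. Keep the other three bullets, and keep the late-onset rule in SAP 17.1.3. Show reactions lasting past Day 7 only in the separate solicited presentation already planned, unless one of the remaining conditions applies.

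If the 7-day rule is intended, declare it in SAP 3.3 as a change from the protocol and say whether the events come from the eDiary or the AE Form, so that all sites are handled alike.

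In SAP 17.1.3, define each post-vaccination interval from the participant's actual vaccination date to that date plus 29 days, which gives 30 days inclusive.

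The cost is a change of SAP wording and interval programming from vaccination dates already recorded. No new data are needed.
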